Taken together, these various clinical studies provide a solid rationale for repeat allogeneic MSC infusions. In no case did the administration of multiple doses lead to a significant increase in the frequency of adverse effects, or to a decrease in therapeutic efficacy over a single dose. In many cases, repeated infusions indeed improved clinical outcomes, demonstrating an additive effect of allogeneic MSC therapy. Given these promising results, investigations are now warranted to determine optimal dosing frequency and total doses of allogeneic MSCs to administer.

It is particularly important to establish safety of repeat doses of allogeneic MSCs in the subject population enrolled in the CRATUS study. These individuals are of older age and are not represented in the previous studies described. In this follow-on study subject s in an earlier open label pilot study will be asked to participate in this repeat dosing protocol.

A.3 STUDY OBJECTIVES AND ENDPOINTS

A.3.1 Study Objectives

A.3.1.1 Primary Objective

1. Demonstrate the safety and tolerability of a second intravenous infusion of allo-hMSCs in subjects with aging frailty who had previously received an infusion of allogeneic MSCs as part of the pilot phase of the protocol.

A.3.1.2 Secondary Objectives

1. To explore treatment efficacy (decrease in frailty, frequency of acute exacerbations, change in symptom related quality of life, improved cardiovascular status, decrease in inflammatory biomarkers, endothelial function and 1 year survival).

A.3.2 Study Endpoints

A.3.2.1 Primary Endpoints (Safety)

1. Safety (Primary): Incidence (at one-month post second infusion) of any treatment-emergent serious adverse events (TE-SAEs), defined as the composite of: death, non-fatal pulmonary embolism, stroke, hospitalization for worsening dyspnea and clinically significant laboratory test abnormalities, determined per the Investigator's judgment.

Laboratory tests included in the primary endpoint include the following:

- Serum chemistry: chloride, sodium, Carbon Dioxide, BUN, creatinine, glucose, calcium, AST/SGOT, ALT/SGPT, total bilirubin (fractionate if total >1.5 times normal), alkaline phosphatase, albumin,
- Hematology (CBC): hemoglobin, hematocrit, platelets, WBC, WBC differential

A.3.2.2 Secondary Endpoints (Efficacy)

The following efficacy endpoints will be evaluated in this trial (During the screening, baseline, Month 3 and/or Month 6 visits):

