A major limitation to the second infusion approach is the small sample size. While it is assumed that all 15 subjects will be eligible for a second infusion, there is a chance that subjects will not want to undergo a second infusion and thus would further limit the amount of information received. However, the second infusion strategy is being implemented to obtain information on the safety of a second infusion of allogeneic MSCs to help guide future studies.

Addendum B: Penicillin/streptomycin free cell safety study

B.1 Rationale and Description for penicillin/streptomycin free cell safety study

This addendum to the protocol is designed to gain additional safety of penicillin/streptomycin free intravenous infusion of allo-hMSCs in subjects with aging frailty. Up to twenty subjects will be recruited to participate in a single dose of allogeneic MSCs in this follow-on phase. All study specific processes and procedures included in the protocol apply in this addendum unless otherwise noted. This population will not be included in the main phase of the trial, which included 15 pilot and 30 randomized subjects. Additionally, subjects receiving a dose in the penicillin/streptomycin free study are eligible to receive up to three (3) additional infusions.

B.2 STUDY OBJECTIVES AND ENDPOINTS

B.2.1 Study Objectives

B.2.1.1 Primary Objective

1. Demonstrate the safety and tolerability of penicillin/streptomycin free intravenous infusion of allo-hMSCs in subjects with aging frailty.

B.2.1.2 Secondary Objectives

6. To explore treatment efficacy (decrease in frailty, frequency of acute exacerbations, change in symptom related quality of life, improved cardiovascular status, decrease in inflammatory biomarkers, endothelial function and 1 year survival).

B.2.2 Study Endpoints

B.2.2.1 Primary Endpoints (Safety)

1. Safety (Primary): Incidence (at one month post second infusion) of any treatment-emergent serious adverse events (TE-SAEs), defined as the composite of: death, non-fatal pulmonary embolism, stroke, hospitalization for worsening dyspnea and clinically significant laboratory test abnormalities, determined per the Investigator's judgment.

- Laboratory tests included in the primary endpoint include the following:

- Serum chemistry: chloride, sodium, Carbon Dioxide, BUN, creatinine, glucose, calcium, AST/SGOT, ALT/SGPT, total bilirubin (fractionate if total >1.5 times normal), alkaline phosphatase, albumin,

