- Hematology (CBC): hemoglobin, hematocrit, platelets, WBC, WBC differential

B.2.2.2 Secondary Endpoints (Efficacy)

The following efficacy endpoints will be evaluated in this trial (During the screening, baseline, Month 3 and/or Month 6 visits):

1. Difference in rate of decline of Frailty defined as:
 - Reduced Activity (assessed via CHAMPS questionnaire)
 - Slowing of Mobility (assessed via a 4 meter gait speed test and SPPB assessment)
 - Weight Loss
 - Diminished handgrip strength (assessed via dynamometer)
 - Exhaustion (assessed via the MFI questionnaire)
 - Decrease in subject quality of life assessment(s) (assessed via ICECAP, SF-36, EQ-5D Questionnaires)
2. Death from any cause.
3. Change between screening and 6 months in dobutamine stress echo induced ejection fraction.
4. Change between screening and 6 months for the following panel of inflammatory markers: CRP, IL-6, D-dimer, fibrinogen, CBC with differential, and TNF α
5. The incidence of each component of the primary endpoint including non-fatal pulmonary embolism, stroke, hospitalization for worsening dyspnea and clinically significant laboratory test abnormalities
6. Change in Smell Identification Test (UPSIT)

B.3 Inclusion and Exclusion Criteria

B.3.1 Inclusion Criteria for penicillin/streptomycin free cell safety study

In order to participate in this study, a subject MUST:

1. Provide written informed consent.
2. Subjects age \geq 60 and \leq 95 years at the time of signing the Informed Consent Form.
3. Show signs of frailty apart from a concomitant condition as assessed

by the Investigator with a frailty score of 4 to 7 using the Canadian Clinical Frailty Scale

4. Female subjects must have an FSH \geq 25.8 mIU/mL, if not currently on hormone replacement therapy.

B.3.2 Exclusion Criteria for penicillin/streptomycin free cell safety study

In order to participate in this study, a subject MUST NOT have any of the following:

1. Score of \leq 24 on the Mini Mental State Examination (MMSE)
2. Inability to perform any of the assessments required for endpoint analysis (report safety or tolerability concerns, perform PFTs, undergo blood draws, read and respond to questionnaires).
3. Active listing (or expected future listing) for transplant of any organ.

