4. Clinically important abnormal screening laboratory values, including but not limited to: hemoglobin <8 g/dl, white blood cell count $<3000/\text{mm}^3$, platelets $<80,000/\text{mm}^3$, INR > 1.5 not due to a reversible cause (i.e. Coumadin), aspartate transaminase, alanine transaminase, or alkaline phosphatase > 3 times upper limit of normal, total bilirubin > 1.5 mg/dl.
5. Serious comorbid illness that, in the opinion of the investigator, may compromise the safety or compliance of the subject or preclude successful completion of the study. Including, but not limited to: HIV, advanced liver or renal failure, class III/IV congestive heart failure, myocardial infarction, unstable angina, or cardiac revascularization within the last six months, or severe obstructive ventilatory defect.
6. Any other condition that, in the opinion of the investigator, may compromise the safety or compliance of the subject or preclude successful completion of the study.
7. Be an organ transplant recipient.
8. Have a clinical history of malignancy within 3 years (i.e., subjects with prior malignancy must be disease free for 3 years), except curatively-treated basal cell carcinoma, squamous cell carcinoma, melanoma in situ or cervical carcinoma if recurrence occurs.
9. Have a non-pulmonary condition that limits lifespan to < 1 year.
10. Have a history of drug or alcohol abuse within the past 24 months.
11. Be serum positive for HIV, hepatitis BsAg or Viremic hepatitis C.
12. Be currently participating (or participated within the previous 30 days) in an investigational therapeutic or device trial.
13. Be a female who is pregnant, nursing, or of childbearing potential while not practicing effective contraceptive methods. Female subjects must undergo

a blood or urine pregnancy test at screening and within 36 hours prior to infusion.

14. Have hypersensitivity to dimethyl sulfoxide (DMSO)

B.4 Dosing

After subjects complete have completed their screening and continue to meet inclusion/exclusion criteria subjects will receive a single infusion of allogeneic penicillin/streptomycin free hMSCs: 1×10^8 (100 million) cells delivered via peripheral intravenous infusion.

The penicillin/streptomycin free Allo-hMSCs will be derived from donors meeting criteria for allogeneic unrelated human bone marrow stem cell source manufactured by the University of Miami or from a commercial clinical grade bone marrow source.

B.5 Dosage Rationale

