The Month 12 visit will be waived if screening visits for subsequent infusions take place prior to this visit.

B.15 Statistical Considerations

All subjects will be offered the penicillin/streptomycin free hMSCs and formal statistical considerations regarding sample size and power are not provided. Based on prior studies, stem cells are safe but strict safety monitoring will be employed to continue the safety assessment of penicillin/streptomycin free allogeneic infusion of MSCs. No detailed analyses will be described in the statistical analysis plan.

B.16 Safety Monitoring of 30-Day Rate of TE-SAEs

Monitoring of the rate of TE-SAEs by 30-days post infusion among subjects who received the infusion of penicillin/streptomycin free allogeneic MSCs will be employed to assist the DSMB in prospective monitoring of this study. The guideline is to be used to indicate boundaries requiring discussion by the DSMB and is designed to assist the independent DSMB in overseeing the study. The DSMB may also request additional interim analyses and develop other criteria including provision for monitoring of potential late effects to determine when to intervene in the enrollment or treatment of subjects in the study. Monitoring of key safety endpoints will be conducted. If rates significantly exceed the pre-set threshold, then the DSMB will be notified.

A Bayesian motivated safety stopping guideline for monitoring the 30-day TE-SAE rate will be used for this trial. The expected underlying rate of TE-SAE at 30 days post-infusion is assumed to be 10% based on the assumption that 2 out of 20 subjects experience a TE-SAE. It would then be assumed that a rate of greater than 40.0% is unacceptable.

A Beta distribution can be used as the prior distribution of θ ; where θ is the proportion of subjects who experience an TE-SAE by 30-days post infusion. The stopping rule is based on the beta-binomial methodology and assumes a prior expected failure rate. This leads to prior Beta parameters where $a=0.8$ and $b=5.2$. The Beta distribution will have a prior mean of 0.13 and a prior probability of <0.05 of exceeding 0.40. The guideline is derived such that there is strong evidence (posterior probability >0.95) that the probability of the event is greater than 40%, the trial will be stopped. The resulting boundaries tabulated in table B2 were rounded to be conservative with the stopping guideline and is considered after 5 subjects are enrolled on the study.

TABLE B2

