D.2.2.1 Primary Endpoints (Safety)

- Safety (Primary): Incidence (at one month post infusion) of any treatment-emergent serious adverse events (TE-SAEs), defined as the composite of: death, non-

fatal pulmonary embolism, stroke, hospitalization for worsening dyspnea and clinically significant laboratory test abnormalities, determined per the Investigator's judgment.

- Serum chemistry: chloride, sodium, Carbon Dioxide, BUN, creatinine, glucose, calcium, AST/SGOT, ALT/SGPT, total bilirubin (fractionate if total >1.5 times normal), alkaline phosphatase, albumin,
- Hematology (CBC): hemoglobin, hematocrit, platelets, WBC, WBC differential

D.2.2.2 Secondary Endpoints (Efficacy)

The following efficacy endpoints will be evaluated in this trial (During the screening, baseline, Month 3 and/or Month 6 visits):

1. Difference in rate of decline of Frailty defined as:
 - Reduced Activity (assessed via CHAMPS questionnaire)
 - Slowing of Mobility (assessed via a 4 meter gait speed test and SPPB assessment)
 - Weight Loss
 - Diminished handgrip strength (assessed via dynamometer)
 - Exhaustion (assessed via the MFI questionnaire)
 - Decrease in subject quality of life assessment(s) (assessed via ICECAP, SF-36, EQ-5D Questionnaires)
2. Death from any cause.
3. Change between screening and 6 months in dobutamine stress echo induced ejection fraction.
4. Change between screening and 6 months for the following panel of inflammatory markers: CRP, IL-6, D-dimer, fibrinogen, CBC with differential, and TNF α
5. The incidence of each component of the primary endpoint including non-fatal pulmonary embolism, stroke, hospitalization for worsening dyspnea and clinically significant laboratory test abnormalities
6. Change in Smell Identification Test (UPSIT)

D.3 Study Design

Subjects who received placebo in the randomized phase of the trial will have the option to receive 1×10^8 (100 million) allogeneic hMSCs, if all study endpoints are met from the randomized phase. Up to ten (10) subjects may be enrolled in this addendum and

subjects will follow the study schedule listed in Section D14 (Table D1) of this addendum.

D.4 Inclusion and Exclusion Criteria

D.4.1 Inclusion Criteria

In order to participate in this study, a subject MUST:

1. Provide written informed consent.
2. Subjects age ≥ 60 and ≤ 95 years at the time of signing the Informed Consent Form for this follow on phase.
3. Have previously participated in the randomized phase of the trial and received placebo.

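### Addendum B gives one infusion, but its primary safety endpoint is anchored to a second; as worded it has no evaluable subjects within the addendum

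*Combined protocol and SAP*

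**What the plan says.** B.1 sets the size and exposure of the sub-study: "Up to twenty subjects will be recruited to participate in a single dose of allogeneic MSCs in this follow-on phase". It keeps these subjects apart from the 15 pilot and 30 randomized subjects. B.4 repeats that "subjects will receive a single infusion of allogeneic penicillin/streptomycin free hMSCs", Table B1 has a single infusion visit (Day 1), and the synopsis calls the Addendum B infusion the initial one, with any further infusions given under Addendum C.

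The sole primary objective, in B.2.1.1, is to "Demonstrate the safety and tolerability of penicillin/streptomycin free intravenous infusion of allo-hMSCs in subjects with aging frailty". The primary endpoint, in B.2.2.1, is "Incidence (at one month post second infusion) of any treatment-emergent serious adverse events (TE-SAEs", followed by the usual composite. Item 5 of B.2.2.2 then refers back to it: "The incidence of each component of the primary endpoint".

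The monitoring section of the same addendum uses a different anchor. B.16 describes "Monitoring of the rate of TE-SAEs by 30-days post infusion among subjects who received the infusion of penicillin/streptomycin free allogeneic MSCs".

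**The concern.** The endpoint is tied to an event that Addendum B does not contain. Followed literally, the primary objective goes unanswered: either the endpoint has no subjects, or it reports events after a later infusion given under another addendum, to whichever subjects choose to continue.

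That later infusion need not be the product under study. The synopsis allows subjects in Addendum C to receive cells with antibiotic, and C.1 says only that the cells may be antibiotic-free. C.1 and C.5 mention antibiotic-containing cells expressly for returning pilot subjects, but the synopsis has no such limit. The month after that infusion is also already the primary endpoint of Addendum C (C.3.2.1), so a literal Addendum B result would repeat part of it.

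No later document is planned to settle the matter. A.16 and C.16 defer detailed analyses to a separate statistical analysis plan, whereas B.15 says that no detailed analyses will be described there. B.2.2.1 is therefore the operative definition.

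**Working it through.** **Which infusion is it?** Inputs: up to 20 subjects (B.1); one infusion each (B.1, B.4, Table B1, synopsis); no earlier study infusion, because the cohort lies outside the main phase (B.1). The Addendum B infusion is therefore number 0 + 1 = 1 for every subject. Addendum B infusions that are a subject's second: 0 of up to 20.

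This does not depend on how many subjects continue. If 0, 10 or 20 of them go on to Addendum C, there are 0, 10 or 20 second infusions, all of them Addendum C infusions. The number of Addendum B infusions whose following month is counted stays at 0 of 20.

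**The endpoint anchors side by side.**

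| Place | What is given there | Anchor of the endpoint or monitoring window |
|---|---|---|
| Synopsis; Section 2.2.1 | one infusion (pilot, randomized) | one month after infusion |
| A.3.2.1 | second infusion in pilot subjects | one month after second infusion |
| B.2.2.1 | one initial infusion | one month after second infusion |
| B.16 | the same infusion as B.2.2.1 | 30 days after infusion |
| C.3.2.1 | later infusions | one month after each additional infusion |
| D.2.2.1 | one cell infusion | one month after infusion |

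B.2.2.1 is the only row in which the anchor does not fit what is given. Its wording is almost that of A.3.2.1 ("Incidence (at one-month post second infusion) of any treatment-emergent serious adverse events (TE-SAEs"), where a second infusion is the subject of study. Section 2.2.1 and D.2.2.1 both read "Incidence (at one month post infusion) of any treatment-emergent serious adverse events (TE-SAEs". The monitoring text was adapted between addenda: A.17 counts from the second infusion, B.16 from the infusion. The endpoint text was not. That the phrase was carried over from Addendum A is an inference.

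**The plan's own figure.** B.16 assumes 2 events in 20 subjects: 2/20 = 10%, which reproduces. At that rate, with 20 treated:
- expected subjects with an event in the 30 days after the Addendum B infusion: 20 × 0.10 = 2.0;
- chance of at least one: 1 − 0.90^20 = 0.878.

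B.2.2.1 as worded targets none of these events.

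**What the corrected endpoint can report** (two-sided exact Clopper-Pearson 95% limits, 20 subjects):
- 0/20: the lower limit is 0; the upper limit is 1 − 0.025^(1/20) = 0.168, so 0% to 16.8%.
- 2/20: the lower limit solves P(X ≥ 2) = 0.025, giving 0.0123; the upper limit solves P(X ≤ 2) = 0.025, giving 0.3170, so 1.2% to 31.7%.

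**The case against.** The strongest reply is that one word is out of line and everything around it shows the intent. The synopsis covers Addendum B and its endpoint row, which is not limited to the main phase, is anchored to the infusion. Section 9.1 puts everyone who received at least one dose into the safety summaries. B.16 defines its event rate at 30 days after the infusion, and Table B1 has a Month 1 visit to match. A sensible analyst would report the right thing.

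Most of this stands. The intended anchor can be recovered, and the proposed denominator is the one Section 9.1 already implies. But none of these places overrides B.2.2.1: B.1 carries over main-protocol processes only unless otherwise noted, and B.2.2.1 notes otherwise. B.16 governs monitoring, not the reported endpoint.

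A second reply is that B.1 and B.14 mention additional infusions, so the second-infusion anchor might be deliberate. The documents place those infusions elsewhere: the synopsis assigns them to Addendum C, whose schedule (Table C1) is the one that repeats. An anchor there would also not address B.2.1.1.

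A third is that incidence at one month after a second infusion could be read as cumulative from the first. That would bring in the first month for subjects who continue, but the endpoint would remain undefined for those who do not.

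**Conclusion.** B.2.2.1 is wrong as written and should be corrected. It is an internal inconsistency, not a questionable design choice. As worded, the month after 0 of up to 20 Addendum B infusions is counted; once corrected, up to 20 of 20. The counts rest on the single-infusion statements in B.1, B.4, Table B1 and the synopsis, and on reading the endpoint as the month after the named infusion. The intervals assume that all 20 subjects are treated and evaluable.

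Three stronger readings are not supported:
- A reader might infer that serious events after the Addendum B infusion go uncollected or unmonitored. They do not: Table B1 schedules adverse event review and laboratory tests at Day 1 and Month 1, and B.16 monitors the 30 days after the infusion. The defect is confined to the reported primary endpoint and, by reference, to secondary endpoint 5.
- A reader might try to state how precise the literal endpoint would be among subjects who continue. The documents give no uptake for this cohort, so no such figure can be given.
- A reader might infer from B.14.1 that a later infusion has to wait for the Month 12 call. The same section lets screening for an additional infusion come first and the call be waived, so no minimum delay can be taken from it.

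**What to change.** In B.2.2.1, replace the reference to a second infusion with one month after infusion of the penicillin/streptomycin-free product. Add one sentence making all subjects who received the Addendum B infusion the denominator, consistent with Section 9.1. Item 5 of B.2.2.2 then follows by reference, and later infusions stay under C.3.2.1.

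Record the change as a dated correction with its reason. C.1 reports that 20 subjects have already received the antibiotic-free dose, so a silent switch at reporting would look like a post-hoc change of primary endpoint.

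The cost is one phrase, one sentence and a note. No visit, laboratory test, data item, dose or schedule changes.
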